5. METHODS

5.1 Study parameters/endpoints

5.1.1 Main study parameters

- Our first primary outcome measure is the QRISK3 score (11). The QRISK3 algorithm (www.qrisk.org/three) calculates a person's risk of developing a cardiovascular event (e.g. a heart attack or stroke) over the next 10 years. The score presents the average risk of people with the same risk factors as those entered for that person. The QRISK3 is the preferred algorithm for assessing cardiovascular risk according to the NICE guideline Cardiovascular Disease (18). It includes severe mental illness and use of atypical antipsychotics as predictors for cardiovascular disease, which makes it suitable for use in our study.

The QRISK3 score is calculated based on age, gender, ethnicity, Townsend deprivation score, smoking status, diabetes status, having chronic kidney disease,

atrial fibrillation, migraines, rheumatoid arthritis, systemic lupus erythematosus, severe mental illness or a family history of premature coronary heart disease in a first degree relative, being on blood pressure treatment, on regular steroid tablets, or on atypical antipsychotic medication, having a diagnosis of or treatment for erectile dysfunction, levels of cholesterol/HDL ratio, systolic blood pressure, standard deviation of blood pressure, and Body Mass Index. As the Townsend deprivation score is not applicable to the Dutch population, we will set this to 0, meaning neither deprived nor affluent, as is advised by the authors. The QRISK3 score can range from 0 to 100%. We consider a decrease of 2.5%-points as clinically relevant.

- Our other primary outcome measure is the Mental Health Inventory, five-item version (MHI-5), which is a measure for the mental quality of life (19). The MHI-5 is a derivative of the 36-item short form health survey, the SF36, and assesses symptoms of depression and anxiety, loss of behavioural or emotional control, and psychological well-being in the prior four weeks. The MHI-5 ranges from 0 to 100, where a score of 100 equals perfect mental health. A score of 60 or higher is seen as good mental health, whereas a score below 60 is seen as poor mental health. We will consider an increase of 5 points as clinically relevant.

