3.3 Exclusion criteria

A potential patient who meets any of the following criteria will be excluded from participation in this study: 1) diagnosis of dementia or organic psychosis, 2) diagnosis of cardiovascular disease (acute myocardial infarction, acute coronary syndrome, heart failure, ischemic stroke, transient ischemic attack, peripheral artery disease, aortic aneurysm or a revascularization procedure, i.e. percutaneous coronary intervention or coronary artery bypass grafting).

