6.2 AEs and SAEs

6.2.1 Adverse events (AEs)

Adverse events are defined as any undesirable experience occurring to a patient during the study, whether or not considered related to the trial procedure or the experimental intervention. All adverse events reported spontaneously by the patient or observed by the general practitioner, his staff, or the investigator will be recorded.

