6.2.2 Serious adverse events (SAEs)

During the control period, patients receive care as usual, so no AE and SAE are expected, and if they do, they are part of the usual care process and cannot be considered a consequence of participating in the study.

We will instruct all general practitioners to warn the investigator about every SAE occurring during the study, i.e. psychosis, (attempted) suicide, requirement of the crisis intervention team, and death. We will examine every case to see whether the trial procedure or the intervention caused the SAE. The investigator will report all SAEs to the sponsor without undue delay after obtaining knowledge of the events.

The sponsor will report the SAEs through the web portal *ToetsingOnline* to the accredited METC that approved the protocol, within 7 days of first knowledge for SAEs that result in death or are life threatening, followed by a period of maximum 8 days to complete the initial preliminary report. All other SAEs will be reported within a period of maximum 15 days after the sponsor has first knowledge of the serious adverse events.

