The MHI-5 consists of five questions with each six answer categories: continuously-mostly-often-sometimes-rarely-never. The answers of the positively formulated questions (questions 3 and 5) will be assigned the values 5, 4, 3, 2, 1, and 0, respectively. The

answers of the negatively formulated questions (questions 1, 2, and 4) will be assigned the values 0, 1, 2, 3, 4, and 5, respectively. Subsequently, a sum score will be calculated, multiplied by 4, resulting in an MHI-5 score ranging from 0 to 100, where a score of 100 equals perfect mental health.

Data analysis will be performed according to the intention-to-treat principle. Data from patients who discontinued follow-up will be included in the analysis up to the point of dropout. Descriptive analyses will be performed to describe the patient characteristics. Mean and standard deviation (std) or median and interquartile range for continuous characteristics and number and percentages for categorical characteristics will be determined. The relationship between treatment and outcome measures measured at 5, 10, 15, and 20 month follow up will be analysed with mixed three level linear or logistic regression, taking into account that the times of measurement are clustered within patients, and patients within general practices. We will perform a model with a random intercept and all other variables fixed. To test the effect of the intervention a model with time, group (intervention or control) and the interaction between time and group will be performed. A value of $p < 0.05$ will be considered statistically significant for all analyses, based on two-sided testing. Analyses will be performed using the Statistical Package for Social Sciences (SPSS, IBM Corp., Armonk, NY) version 25.

We will present QRISK3 scores and MHI-5 scores as means (SDs) for every measurement point, with notification of the number of patients included in the calculation.

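### The SAE list in section 6.2.2 leaves out non-fatal heart attack, stroke and the other cardiovascular events of section 3.3; secondarily, section 7.1 has no QRISK3 rule after such an event

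*Protocol*

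**What the plan says.** **Outcome and population.** Section 5.1.1 makes QRISK3 the first primary outcome, as the "risk of developing a cardiovascular event (e.g. a heart attack or stroke) over the next 10 years". The listed inputs include smoking, "levels of cholesterol/HDL ratio, systolic blood pressure, standard deviation of blood pressure, and Body Mass Index", and also "being on blood pressure treatment, on regular steroid tablets, or on atypical antipsychotic medication". A previous heart attack or stroke is not an input. Section 3.3 excludes patients with a "diagnosis of cardiovascular disease (acute myocardial infarction, acute coronary syndrome, heart failure, ischemic stroke" and several further cardiovascular conditions. That criterion applies at entry only.

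**Safety.** Section 6.2.2 tells GPs to alert the investigator to all SAEs and defines them: "i.e. psychosis, (attempted) suicide, requirement of the crisis intervention team, and death". Each case is then examined for causality and reported to the ethics committee, within 7 days if fatal or life-threatening and within 15 days otherwise. For AEs in general, section 6.2.1 says "All adverse events reported spontaneously by the patient or observed by the general practitioner, his staff, or the investigator will be recorded", and section 5.1.2 counts the number and type of (S)AEs as a secondary parameter. Section 6.4 provides no DSMB and no interim analysis.

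**Analysis.** Section 7.1 applies intention to treat and adds: "Data from patients who discontinued follow-up will be included in the analysis up to the point of dropout". It gives item-by-item rules for scoring QRISK3, but none for a patient who has a cardiovascular event after inclusion.

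**The concern.** The SAE instruction is wide in its first words and narrow in its definition. The list is introduced as a definition, not as examples, so a GP can follow it to the letter and not notify a non-fatal heart attack, stroke or other event of the section 3.3 type. These are the events the trial aims to prevent. TACTIC can also lead to changes in antipsychotic, blood pressure and lipid medication (section 4), and the protocol's introduction links antipsychotics to cardiac toxicity. Without a DSMB, the 6.2.2 route is the protocol's only stated mechanism for prompt case-by-case review. What is at stake is whether such events reach that review.

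The secondary issue is the meaning of the primary outcome. QRISK3 is used here as a score for people free of cardiovascular disease. After an event, its premise no longer holds for that patient, yet the score can still be calculated. If risk factors improve under post-event care, the patient may appear to have gained.

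**Working it through.** **1. The safety passages side by side.**

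- Opening instruction in 6.2.2: all SAEs.
- Definition in the same sentence: psychosis, (attempted) suicide, need for the crisis team, death.
- Next paragraph: a 7-day deadline for SAEs that are fatal or life-threatening, and 15 days for the rest.
- A fatal heart attack or stroke falls under death and is covered. A non-fatal one is not covered, however severe.
- Sections 6.2.1 and 5.1.2: a non-fatal event known to the GP is recorded as an AE and counted by type. It is therefore captured, but outside notification, causality review and ethics committee reporting.

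**2. How many events.** The documents give no expected event count to reproduce. The inputs from them are 480 patients in four steps (480/4 = 120 per step, taking equal steps), one to four follow-ups at 5-month intervals (5, 10, 15 or 20 months), and an entry risk of at least 5%. The mean 10-year risk p is not stated, so a range is assumed, with constant hazard and a score that is correct on average.

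Hazard per year h = −ln(1 − p)/10. Expected events per step = 120 × (1 − exp(−h × months/12)).

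| Assumed p | h | 5 mo | 10 mo | 15 mo | 20 mo | Total |
|---|---|---|---|---|---|---|
| 5% (entry floor) | 0.00513 | 0.26 | 0.51 | 0.77 | 1.02 | 2.6 |
| 10% | 0.01054 | 0.53 | 1.05 | 1.57 | 2.09 | 5.2 |
| 15% | 0.01625 | 0.81 | 1.61 | 2.41 | 3.21 | 8.0 |
| 20% | 0.02231 | 1.11 | 2.21 | 3.30 | 4.38 | 11.0 |

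These totals include fatal events, which are already reportable. Section 3.3 names more conditions than heart attack and stroke, so the count for its full list could be somewhat higher.

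**3. Effect on mean QRISK3.** Assume that every event is survived, the patient stays in follow-up, and the score falls by 5 points (an assumption).

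- Per patient: 5.2 × 5/480 = 0.05 and 11.0 × 5/480 = 0.11 point. Against the 2.5-point target this is about 2% and 5%.
- Counting only visits after the event: follow-up visits total 120 × (1 + 2 + 3 + 4) = 1,200. Let F(m) be the probability of an event by month m. The shift is 5 × 120 × [4F(5) + 3F(10) + 2F(15) + F(20)]/1,200. At 10% the bracket is 0.0873, giving 0.04 point. At 20% it is 0.1838, giving 0.09 point.
- Outer limit, not the trial's schedule: 20% risk, all 480 patients followed for 20 months (17.5 events) and a 10-point fall give 17.5 × 10/480 = 0.36 point, about 15% of the target.

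**4. Direction.** Lower smoking, cholesterol ratio, blood pressure or BMI after the event lowers the score. Newly started blood pressure treatment, atrial fibrillation, chronic kidney disease or diabetes are listed predictors too. Section 7.1 back-fills blood pressure treatment only when TACTIC is the reason for starting it, so treatment started because of the event enters as a new predictor. The sign of the net change is not fixed.

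**The case against.** **On the SAE list.** The list fits the risk that the protocol itself names, mental destabilisation after a medication change. The deadline for life-threatening SAEs is not empty without cardiovascular events, since attempted suicide can be life-threatening. Cardiovascular events known to the GP are in any case recorded and counted as AEs. All of this is correct, and it means that the events are not invisible and that the two paragraphs do not strictly exclude each other. It does not remove the mismatch between an instruction covering all SAEs and a definition that leaves out a non-fatal heart attack. AE recording also does not carry the review and reporting steps of 6.2.2.

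**On QRISK3.** Handling of scores after an event is commonly settled in the SAP, which is not at hand. Dropping observed scores from the main analysis would depart from intention to treat and from the aim in section 5.6 to keep collecting data. The investigator may also withdraw a patient for urgent medical reasons (section 5.4). These points stand, and they are why the main analysis should not be changed.

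**A stronger reading.** A reader might infer that a patient who has a heart attack and is then treated is scored as a TACTIC success, always in TACTIC's favour. The documents do not support this:

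- The score must actually fall, and treatment started because of the event can raise it.
- Success as a category exists only in the sub-analysis of section 7.3 and needs a fall of 2.5 points.
- Table 1 places all follow-up after TACTIC, but section 6.2.2 speaks of a control period, section 5.5 of patients in a given condition, and section 7.1 models both groups. The design figure is not shown. An event in control time with a falling score would work against TACTIC.

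Nor are the events absent from the outcomes. They are not listed separately, but they fall under the (S)AE parameter.

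**Conclusion.** The main point holds on the wording of the protocol alone and rests on no assumption: the closed list in 6.2.2 omits the non-fatal cardiovascular events of section 3.3, and a GP who follows it would not send them for causality review and ethics committee reporting. The number concerned is modest. It is about 5 to 11 first events at an assumed mean risk of 10–20% and 2.6 at the entry floor of 5%, with fatal events included in both.

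The QRISK3 point is secondary. Section 7.1 has no rule after an incident event, so such a patient can, but need not, be scored as improved. The shift in the mean is about 0.05–0.1 point under an assumed 5-point fall, its direction is uncertain, and it is unlikely to alter the primary conclusion. The issue is what the score means after an event, not material bias.

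**What to change.** 1. **Section 6.2.2.** Reconcile the list with the instruction to notify all SAEs and with the clause on life-threatening SAEs, so that incident events of the kinds named in section 3.3 are covered.
2. **Section 5.1.2.** Within the existing (S)AE parameter, state that first cardiovascular events will be tabulated by condition.
3. **Section 7.1 or the SAP.** Keep the intention-to-treat analysis of QRISK3 as the main analysis. Add one sensitivity analysis that omits QRISK3 scores recorded after a first event of the section 3.3 kind. MHI-5 and the other outcomes are unaffected.

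The cost is protocol wording, an event date from GP records that the study already uses, and a few more SAE reports. The sensitivity analysis omits a small number of scores and relies on those being missing at random, which is why it should not replace the main analysis.

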5.1.2 Secondary study parameters

- Health-related quality of life will be measured with the EuroQol-5D-5L (EQ-5D). This instrument is available in a validated Dutch translation. The EQ-5D comprises five domains: mobility, self-care, usual activities, pain/discomfort, and anxiety/depression. The EQ-5D index is obtained by applying predetermined weights to the five domains, and ranges from 0 to 1, where a score of 1 equals perfect health.
- We will measure change in side effects using the Liverpool University Neuroleptic Side Effect Rating Scale (LUNSERS) (17).
- We will use the 8-item Client Satisfaction Questionnaire (CSQ-8) to measure participants' satisfaction with care. This questionnaire is recommended for use in psychiatric patients (20),(21) and has a Dutch validated version (22).
- Number of groups meetings (Step 1), multidisciplinary meetings (Step 2), and GP contacts (Step 3);
- Number and content of individualized treatment plans;
- Percentage of patients who attend group meeting (Step 1);
- Percentage of patients who attend multidisciplinary meeting (Step 2);
- Percentage of patients who contact GP to discuss individualized treatment plan (Step 3);

- Reasons for drop-out.
- Numbers and type of (serious) adverse events.
- Numbers and type of advice given in Step 3 of the intervention, and numbers and type of advice followed up or executed.
- Healthcare utilization as measured with the Dutch version of the Treatment Inventory of Costs in Patients with psychiatric disorders (TIC-P) questionnaire;
- Costs related to health care, such as medication, visits to the general practice, visits to relevant medical specialists.
- Patient costs, such as travel costs, time costs and over the counter medication
- Costs in other sectors, such as health promotion costs within budget of municipalities

5.2 Randomisation, blinding and treatment allocation

Clusters will be randomised to either of the four steps, or cluster groups, as described in figure 1. The randomisation program we will use, will be custom made by an investigator with no clinical involvement in the trial. Blinding and treatment allocation are not applicable, as it is not possible to blind clusters.

5.3 Study procedures

After enrolment of the general practice, a list with all eligible patients will be generated in VIPlive. A computerized programme will randomly select 30 eligible patients per general practice, who will receive a letter from their general practitioner, informing the patient about the upcoming trial. Patients will be invited to contact the general practice when they are interested in participation. An appointment for a regular cardiovascular risk management consultation at the general practice will then be made. Patients who did not reply to the letter, will be contacted by phone. In the context of the existing regional cardiovascular risk management programme patients will undergo physical examination (for measuring length, weight and blood pressure), venapuncture and urinalysis (for measuring risk factors, i.e. HbA1c, blood glucose, lipid spectrum and kidney function), and will be asked about their ethnicity, smoking status and family history of coronary heart disease. All other information will be derived from their medical file, e.g. having atrial fibrillation, migraines, or rheumatoid arthritis. In addition to the usual SCORE calculation, the QRISK score will also be calculated specifically for this study. When the QRISK3 score is below 5%, the patient does not meet the inclusion criteria and will be followed by the general practitioner according to the regular cardiovascular risk management

programme. Patients with a QRISK3 $\geq 5\%$ will be invited to sign informed consent for participation in the TACTIC intervention study.

After signed informed consent and inclusion, baseline measurement will take place and patients will fill in a digital questionnaire using Castor EDC, containing MHI-5, EQ-5D-5L, TIC-P and LUNSERS. As part of the preparation for the multidisciplinary meeting, patients will be asked to fill in a custom-made questionnaire on antipsychotic use. This questionnaire will help healthcare professionals prepare for the meeting and will give the patient insight in possible topics that can be addressed during the meeting. In case patients do not have an email address, we will send the questionnaires by mail. Patients will then watch the information video at home, attend the multidisciplinary meeting, and attend a consultation with their general practitioner, as described in section 5. At five months follow-up, patients will be invited for follow-up (monitoring) measurements at the general practice as part of the regular regional cardiovascular risk management programme (usual care), to undergo physical examination (measuring weight and blood pressure), venapuncture and urinalysis (for measuring risk factors, i.e. HbA1c, blood glucose, lipid spectrum and kidney function). As part of the evaluation, patients will also fill in questionnaires, containing MHI-5, EQ-5D-5L, LUNSERS, TIC-P and general questions about smoking status and family history of coronary heart disease. Depending on which step the cluster has started, patients will undergo one to four follow-up measurements, every five months. This is in line with the routine check-ups patients will have in the regular cardiovascular risk management programme. During the last follow-up measurement, they are also asked to fill in the CSQ-8. Table 1 presents the schedule of assessments.

No diagnostic procedures or treatment will be postponed.

	Visit general practice	Digital information	Physical examination	Laboratory tests	Questionnaires
Week 1 Routine screening and inclusion after informed consent	X		X	X	
Week 2 Baseline measurement					X
Week 3 Information video		X			
Week 4/5	X				

Multidisciplinary meeting					
Week 5/6 Consultation with GP	X				
Month 5 Routine consultation as part of usual care. Follow-up measurement 1 Start Step 2 at Week 1	X		X	X	X
Month 10 Routine consultation as part of usual care. Follow-up measurement 2 Start Step 3 at Week 1	X		X	X	X
Month 15 Routine consultation as part of usual care. Follow-up measurement 3 Start Step 4 at Week 1	X		X	X	X
Month 20 Routine consultation as part of usual care. Follow-up measurement 4 Finish Follow-up all clusters	X		X	X	X

Table 1. Schedule of assessments.

5.4 Withdrawal of individual subjects

Patients can leave the study at any time for any reason if they wish to do so, without any consequences. If a patient moves to a different general practice during the study, the patient will be excluded from analysis from the moment of changing practice.

The investigator can decide to withdraw a patient from the study for urgent medical reasons. If a patient withdraws from the study, they will continue to receive care as usual.

5.5 Replacement of individual subjects after withdrawal

Patients can be replaced in case of withdrawal of another patient, provided that coming measurements are under the same conditions as they would be for the withdrawing

patient, i.e. when a patient is in the intervention condition at the time of withdrawal, this patient can only be replaced by a patient who is also in the intervention condition.

5.6 Follow-up of subjects withdrawn from treatment

In case of withdrawal from treatment, we will strive to collect all necessary data for analysis, unless, of course, informed consent is also withdrawn. This is according to the intention-to-treat principle.

5.7 Premature termination of the study

The study will be terminated in its current design as recruitment of the necessary number of cluster fails.

In case the study will be terminated prematurely, we will fill in the form “Melden beëindiging studie” on www.ccmo.nl and notify the medical research ethics committee within 15 days.

6. SAFETY REPORTING

6.1 Temporary halt for reasons of subject safety

In accordance to section 10, subsection 4, of the WMO, the sponsor will suspend the study if there is sufficient ground that continuation of the study will jeopardise patient health or safety. The sponsor will notify the accredited METC without undue delay of a temporary halt including the reason for such an action. The study will be suspended pending a further positive decision by the accredited METC. The investigator will take care that all patients are kept informed.

